13.2 DESCRIPTIVE ENDPOINTS

The following endpoints will be summarized using descriptive statistics.

Rate of ischemic stroke or systemic embolism through 5 years post-implant:

Kaplan-Meier survival analysis will be used to estimate the rate of ischemic stroke or systemic embolism through 5 years post-implant. Subjects who receive an implant of the ACP device will be included in the analysis.

Occurrence of composite of damage to blood vessel or organ or damage to adjacent organs at implant, device dislodgement, device fracture, device erosion or pericardial tamponade through 5 years post-procedure :

Kaplan-Meier survival analysis will be used to estimate the rate of occurrence of the composite of device dislodgement, device fracture, device erosion, pericardial tamponade, damage to blood vessel or organ at implant access or damage to adjacent organs through 5 years post procedure. Subjects who receive an implant of the ACP device will be included in the analysis.

Device success rate- defined as device deployed and implanted in correct position:

The count and proportion of subject with device success will be summarized. Subjects who receive an implant of the ACP device will be included in the analysis.

Rate of closure of the LAA - defined as residual jet around the device of $\leq 5\text{mm}$, based on the 45-day TEE:

The count and proportion of subject with closure of the LAA will be summarized. Subjects who receive an implant of the ACP device will be included in the analysis.

Reporting:

The following data will be summarized and reported annually to CFDA.

- Investigator sites and enrollment status
- Demographic and baseline characteristics
- Serious Adverse events
- Protocol deviation

Clinical Investigational Plan

- Procedural results (procedure success, implanted device size, procedure duration)
- Device closure

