5.3.2 Additional Objectives

- (1) To evaluate the occurrence of ischemic stroke or systemic embolism through 5 years in Chinese population implanted with AMPLATZER™ Cardiac Plug
- (2) To evaluate long term safety of AMPLATZER™ Cardiac Plug implantation in Chinese population through 5 years
- (3) To evaluate the immediate successful implantation rate of the AMPLATZER™ Cardiac Plug in the left atrial appendage (LAA)

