5.4.2 Descriptive Endpoints

1. Rate of ischemic stroke or systemic embolism through 5 years post-implant
2. Occurrence of composite of damage to blood vessel or organ or damage to adjacent organs at implant, device dislodgement, device fracture, device erosion, or pericardial tamponade through 5 years post-procedure
3. Device success rate- defined as device deployed and implanted in correct position
4. Rate of closure of the LAA - defined as residual jet around the device of ≤ 5mm, based on the 45-day TEE

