7.1 SCREENING & ENROLLMENT & BASELINE VISIT

The following baseline and enrollment activities are performed as part of the screening process:

- Informed consent process
- Physical examination
- Cardiovascular and medical History
- CHA₂DS₂-VASc score

CHA₂DS₂-VASc	Score
Congestive heart failure/LV dysfunction	1
Hypertension	1
Age \geq 75	2
Diabetes mellitus	1
Stroke/TIA/TE	2
Vascular disease [prior myocardial infarction, peripheral artery disease or aortic plaque]	1
Age 65-74	1
Sex category [i.e. female gender]	1

- HAS-BLED score:

HAS-BLED	Score
Hypertension history (uncontrolled, > 160 mmHg systolic)	1
Abnormal renal function/renal disease (dialysis transplant, creatinine > 2.6 mg/dL or > 200 μ mol/L)	1

Clinical Investigational Plan

Liver disease (cirrhosis, bilirubin > 2x normal AST/ALT/AP > 3x normal)	1
Stroke history	1
Bleeding, anemia, or predisposition to bleeding	1
Labile INR (Unstable/high INR's, or poor time (< 60% time in therapeutic range)	1
Elderly - Age \geq 65 years	1
Drugs - Medication usage predisposing to bleeding (antiplatelet agents, NSAIDs)	1
Alcohol usage history (> 8 drinks/week)	1

- 12-lead ECG
- TEE (optional if a TEE is performed on the day of procedure)
- Antithrombotic medication assessment
- Neuroimaging (brain MRI or CT scan)
- Modified Rankin Scale

The principal investigators or delegated study personnel are responsible for screening all potential subjects to determine subject eligibility for the study. If a subject does not meet all inclusion criteria or meets any of the exclusion criteria, the subject cannot participate in the study and cannot be enrolled. The subject is enrolled in the study when consent has been obtained and the dilator/delivery system is introduced.

Enrollment information (name of the study, date of consent and enrollment criteria, etc.) will be recorded in the hospital records and eCRF. Complete and submit the screening eCRF in a timely manner (recommended within 5 days). Notification of enrollment to the sponsor will take place only when the sponsor receives the Screening eCRF form.

The following terms will be used to describe potential study participants who do not fully implement the study:

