- **Consented Screen Failure** - Subjects who sign the Informed Consent Form but do not meet the eligibility criteria. These subjects will not be considered enrolled in the study. Document the enrollment information (name of the study, date of consent and enrollment criteria, etc.) in the hospital records; complete the Screening form.
- **Enrolled Subject – Unsuccessful implant** - Subjects are enrolled but the device was not implanted. The subject will be withdrawn 7 days after procedure. Document the enrollment information (name of the study, date of consent and enrollment criteria, etc.) in the hospital records; The Baseline, Screening, Procedure, Out of service and Withdrawal eCRFs should be completed (withdrawal should occur at least 7 days after the attempted procedure).

Adverse events will be reported from the time the dilator/device delivery system has been introduced to the time the subject concludes the study. An Adverse Event eCRF should be completed, as applicable.

Clinical Investigational Plan

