13.1.1 Primary safety endpoint (Short Term)

The short term safety endpoint is the proportion of subjects who experience an major adverse events (short term occurrence of death, stroke (ischemic or haemorrhagic), systemic embolism, or procedure or device-related complications requiring major cardiovascular or endovascular intervention) 7 days after the procedure.

Hypothesis:

$$H_0: p_s \geq PG_s$$

$$H_1: p_s < PG_s$$

Clinical Investigational Plan

where p_s is the proportion of subjects undergoing the ACP LAA closure procedure, who experience an acute safety endpoint event. [REDACTED]

[REDACTED]

[REDACTED]

The performance goal, PG_s , in this hypothesis is set at 10%.

[REDACTED]

[REDACTED]

[REDACTED]

[REDACTED]

[REDACTED]

[REDACTED]

[REDACTED]

[REDACTED]

[REDACTED]

Analysis Methods:

The proportion of subjects experiencing a primary safety endpoint, p_s , will be estimated from the binomial model. [REDACTED]

[REDACTED]

[REDACTED]

[REDACTED]

The performance goal assumes that LAA closure occurs in isolation of other cardiac procedures. If the short-term primary safety endpoint is not met, then an additional analysis may be performed excluding subjects who had a cardiac ablation performed in combination with the ACP LAA closure procedure. Excluding subjects who had a cardiac ablation performed in combination with the LAA closure procedure may result in a substantially smaller sample size to evaluate this endpoint; therefore, in this additional analysis, the point estimate for the short-term primary safety endpoint will be descriptively compared to the performance goal, PG_s .

Sample Size Determination:

Sample sizes are calculated assuming an event rate of 5%. The sample size required to reject the null hypothesis with 80% power at the 2.5% significance level is 231 subjects.

Analysis Population:

Enrolled subjects will be included in this analysis.

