13.1.2 Primary safety endpoint (Long-Term)

The long-term safety endpoint is the 2-year occurrence of device embolization, device erosion, clinically significant device interference with surrounding structure, device thrombus, device fracture, device infection (endocarditis / pericarditis), device perforation, device laceration, or device allergy.

[REDACTED]

[REDACTED]

Clinical Investigational Plan

Hypothesis:

$$H_0: p_l \geq PG_l$$

$$H_1: p_l < PG_l$$

where p_l is the long-term safety endpoint event rate. It is assumed that the long-term safety endpoint event rate is 5%. [REDACTED]

[REDACTED]

[REDACTED]

[REDACTED] An event rate of 5% is assumed for the long-term safety endpoint for the ACP device [REDACTED]

[REDACTED] The performance goal, PG_l , is set at 10% [REDACTED]

[REDACTED]

[REDACTED]

[REDACTED]

Analysis Methods:

Kaplan-Meier survival analysis will be used to estimate the event rate of at 24 months (731 days post implant). [REDACTED]

[REDACTED]

Sample Size Determination:

The sample size is estimated assuming an event rate of 5%. A sample size of 231 subjects followed through 24 months will provide 80% power at the 2.5% significance level. Assuming an attrition rate of 25% through 24 months, 308 subjects are required to be enrolled in the study.

Analysis Population:

Enrolled subjects will be included in this analysis.

13.1.3 Primary effectiveness endpoint:

The primary effectiveness endpoint is the composite endpoint of ischemic stroke or systemic embolism at 2 years.

Hypothesis:

$$H_0: p_e \geq PG_e$$

$$H_1: p_e < PG_e$$

where p_e is the event rate at 24 months. [REDACTED]

[REDACTED]

[REDACTED]

[REDACTED] The performance goal, PG_e is set at 9%, [REDACTED]

[REDACTED]

[REDACTED]

Analysis Methods:

[REDACTED]

Clinical Investigational Plan

Kaplan-Meier survival analysis will be used to estimate the event rate of at 24 months (731 days post implant). XXXXXXXXXX

Sample Size Determination:

A sample size of 257 subjects followed through 24 months will provide 80% power at the 2.5% significance level assuming a 24-month event rate of 4.5%. Assuming an attrition rate of 25% through 24 months, 343 subjects are required to be enrolled in the study.

Analysis Population:

Enrolled subjects who receive an implant of the ACP device will be included in the analysis.

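### The 5-year safety composite counts injuries from the implant procedure but leaves out enrolled subjects whose implant failed, which can bias the rate downward

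*Combined protocol and SAP*

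**What the plan says.** Section 5.4.2 lists as a descriptive endpoint: "Occurrence of composite of damage to blood vessel or organ or damage to adjacent organs at implant", together with device dislodgement, fracture, erosion and pericardial tamponade, through 5 years after the procedure. Section 13.2 repeats the components, specifies Kaplan-Meier estimation and fixes the population: "damage to adjacent organs through 5 years post procedure. Subjects who receive an implant of the ACP device will be included in the analysis".

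Section 7.1 sets the point of enrolment earlier than the implant: "The subject is enrolled in the study when consent has been obtained and the dilator/delivery system is introduced". It then defines an enrolled group with an unsuccessful implant: "Subjects are enrolled but the device was not implanted. The subject will be withdrawn 7 days after procedure". Safety data exist for that group, because "Adverse events will be reported from the time the dilator/device delivery system has been introduced".

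The composite is the listed endpoint that matches the second additional objective in section 5.3.2, long-term safety of "Cardiac Plug implantation in Chinese population through 5 years". That objective is not limited to implanted subjects, whereas the first additional objective (stroke or systemic embolism) is.

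Both primary safety endpoints use a wider population. In 13.1.1 the parameter "is the proportion of subjects undergoing the ACP LAA closure procedure, who experience an acute safety endpoint event", and the analysis population is enrolled subjects. In 13.1.2 the statement is "Enrolled subjects will be included in this analysis".

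**The concern.** Membership of the analysis set is decided after enrolment, by whether the implant succeeded. Three kinds of event in the composite (tamponade, vessel or organ damage at access, adjacent-organ damage) can occur before the device is placed and can end the attempt. The outcome being counted can thus remove the subject from the set in which it is counted. Time zero is the procedure, but the population is defined by the result of the procedure.

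Nothing else in the plan brings these subjects back into this rate. A reader of the final report would reasonably take the composite as the procedural and device complication rate of ACP implantation through 5 years, when it is the rate given a completed implant.

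**Working it through.** **Figure to reproduce.** None. The plan states no expected rate, precision or sample size for this endpoint, and no implant-failure rate. The numbers below only scale the effect.

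**Formula.** Let f be the share of enrolled subjects with a failed implant, and let rI and rF be the composite rates in implanted and failed subjects.

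- Implanted-only rate = rI
- All-enrolled rate = (1 − f) × rI + f × rF
- Shortfall of the implanted-only rate = f × (rF − rI)

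The shortfall is positive if rF > rI, zero if they are equal, and negative if rF < rI.

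**Inputs.** 343 enrolled (section 13.3). Assumed: 10 events among implanted subjects, and 0, 10 or 17 failed implants with varying numbers of events.

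| Failed implants | Events among failures | Implanted-only | All enrolled | Difference (points) |
|---|---|---|---|---|
| 0 | – | 10/343 = 2.92% | 10/343 = 2.92% | 0 |
| 10 | 0 | 10/333 = 3.00% | 10/343 = 2.92% | −0.09 |
| 10 | 1 | 3.00% | 11/343 = 3.21% | +0.20 |
| 10 | 5 | 3.00% | 15/343 = 4.37% | +1.37 |
| 17 | 0 | 10/326 = 3.07% | 10/343 = 2.92% | −0.15 |
| 17 | 1 | 3.07% | 11/343 = 3.21% | +0.14 |
| 17 | 8 | 3.07% | 18/343 = 5.25% | +2.18 |

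Check of the last row by the formula: 17/343 × (8/17 − 10/326) = 0.0496 × (0.4706 − 0.0307) = 2.18 points.

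**Break-even.** The two rates agree when events among failures = failures × implanted rate: 10 × 3.00% = 0.30, or 17 × 3.07% = 0.52. One event among the failures is above both.

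**Kaplan-Meier version.** Assume 7 of the 10 events are procedural and 3 late, the plan's 25% attrition is spread over 24 months, the remaining subjects are followed for 5 years, and event-free failures are censored at day 7.

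- 10 failures: 3.23% implanted-only, against 3.17%, 3.46% and 4.62% with 0, 1 and 5 events among the failures.
- 17 failures: 3.31% implanted-only, against 3.20%, 3.49% and 5.51% with 0, 1 and 8 events.

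The differences run from −0.11 to +2.20 points, close to the crude ones.

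**Wider inputs.** With f from 2% to 10%, rI of 3% or 5%, and rF from 15% to 50%, the shortfall runs from 0.2 points (0.02 × (0.15 − 0.05)) to 4.7 points (0.10 × (0.50 − 0.03)). If failures had no events, the implanted-only rate would instead be too high by 0.06 to 0.5 points.

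**The case against.** **The endpoint decides nothing.** It is descriptive and carries no hypothesis, performance goal or success criterion. This stands, and it limits the weight of the point.

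**The worst events are already counted in the right population.** The short-term primary endpoint covers all enrolled subjects for 7 days, which is about as long as failed implants are followed. It captures death, stroke, systemic embolism and complications needing major cardiovascular or endovascular intervention. Adverse events are collected from introduction of the delivery system, and serious ones are reported annually. This stands too, but it is partial. Access-site injuries of the kind listed in Appendix G (fistula, haematoma, aneurysm) that need no major intervention would, in a failed implant, count in neither that endpoint nor this composite.

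**An implanted-only 5-year curve is a legitimate target.** Dislodgement, fracture and erosion need a device in place, and failed implants leave at about day 7. That is a good reason for the device components and no reason for the procedural ones.

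**The long-term primary endpoint is a weak comparator.** Its components are device events, and its 24-month time point is counted from implant, which a non-implanted subject does not have. Agreed; the sound comparator is 13.1.1.

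**The upper scenarios are extreme.** They need 5 of 10 (50%) or 8 of 17 (47%) failed implants to have an event. One event moves the rate by only 0.14 to 0.20 points, far less than the sampling error (10/333 has an exact 95% interval of 1.4% to 5.5%). That is fair as to size. But sampling error does not excuse a bias that comes from the population definition and can be removed at almost no cost.

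**Censoring failed implants at day 7 gives them the later device hazard.** True in principle, but small. With 17 event-free failures, all 3 late events after month 24, and 326 − 7 − 81.5 = 237.5 implanted subjects at risk, keeping the failures in the risk set would change the late increment from about 3/237.5 = 1.26% to 3/254.5 = 1.18%, or 0.08 points.

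**Conclusion.** The concern holds. As written, section 13.2 drops procedural injuries in failed implants from the rate that answers the 5-year safety objective. The direction is downward if failed implants have more events than completed ones. That is plausible, since an injury can end the attempt, but the documents contain no data on it.

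On the main illustration the effect is −0.15 to +2.2 points, zero if no implant fails, and near the bottom of that range if only one failed implant has an event. All of this rests on assumed failure and event counts. The gap is in this one descriptive rate: the events stay in the study's safety data, and the primary analyses are untouched. It should be corrected, but it does not threaten the study's conclusions.

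**What to change.** In section 13.2, change the population of this composite to all enrolled subjects, with time zero at the procedure and unsuccessful implants censored at withdrawal (day 7 or later). Add an implanted-only estimate of dislodgement, fracture and erosion as a supplement, and state that beyond the withdrawal of the failed implants the curve reflects implanted subjects only.

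An equally good variant is to keep the implanted-only 5-year curve and add a count and proportion, in all enrolled subjects, of the procedural components (tamponade, vessel or organ damage at access, adjacent-organ damage). The number of failed implants, and of events among them, should be shown either way.

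The cost is one sentence and one table. No new data are needed. The reported rate may rise slightly, and the all-enrolled rate mixes procedural risk in everyone with device risk in implanted subjects only; the supplement separates the two.

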In a comparative study between the AMPLATZER Cardiac Plug and the WATCHMAN devices (40 patients each), Chun et al.³² found the devices to perform similarly. The rate of successful implantation achieved with the ACP device was greater than with the WATCHMAN device (100% vs. 95%) although the difference was not statistically significant. TEE at follow-up revealed a significantly higher incidence of residual peri-device flow (jet > 5 mm) for the WATCHMAN device compared to the ACP device, although this was not associated with an increased incidence of thromboembolic events. This finding is consistent with other reports on the ACP device³³.

Clinical Investigational Plan

In conclusion, percutaneous LAAO devices have emerged as an alternate option for stroke risk reduction in non-valvular AF patients at high risk for stroke or not suitable for long-term oral anticoagulant.

Certificate History

Date	Action
29 September 2015	CFDA license
16 October 2012	CE Mark

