6.2 DEVICE ACCOUNTABILITY (if applicable)

The ACP device has been approved by CFDA and is commercially released in China. Therefore, there are no additional tracking requirements for this study. Information regarding opened, introduced, and implanted devices will be recorded in the Procedure eCRF and out of service eCRF in case of explant.

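### Device success is computed only among subjects who received an implant, so it cannot register failed implants and does not estimate the implantation rate named in Additional Objective 3

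*Combined protocol and SAP*

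**What the plan says.** Additional Objective 3 (section 5.3.2) concerns how often implantation succeeds immediately; the synopsis version adds that this is judged at the procedure. The listed endpoint that corresponds to it is in section 5.4.2: "Device success rate- defined as device deployed and implanted in correct position".

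Section 13.2 fixes the analysis and the population in two sentences: "The count and proportion of subject with device success will be summarized. Subjects who receive an implant of the ACP device will be included".

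Section 7.1 sets the point of enrolment before the outcome of the implant attempt is known: "The subject is enrolled in the study when consent has been obtained and the dilator/delivery system is introduced". The same section defines a category for unsuccessful implants, described as follows: "Subjects are enrolled but the device was not implanted". For these subjects it requires the Baseline, Screening, Procedure, Out of service and Withdrawal eCRFs. Section 6.2 adds: "Information regarding opened, introduced, and implanted devices will be recorded in the Procedure eCRF".

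For the short-term safety endpoint, section 13.1.1 uses the wider population: "Enrolled subjects will be included in this analysis".

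**The concern.** A rate of successful implantation has to count the attempts that failed. Under section 13.2 a subject must already have an implant to enter the calculation, so the failures that the objective is about are removed before the proportion is formed. The only failure the statistic can still record is a device that was implanted but wrongly positioned.

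At stake is the answer to one named study objective. A reader of the final report could take a figure at or near 100% as evidence that implantation almost always succeeds, when the figure carries no information on that. No hypothesis test depends on it.

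**Working it through.** **Inputs from the documents**
- Outcome definition: section 5.4.2. Population: section 13.2, implanted subjects only.
- Enrolment point and the unsuccessful-implant category: section 7.1.
- Planned enrolment: 343 (sections 5.2.1 and 13.3).
- The only ACP implantation figure: 100% in a comparison with 40 patients per device (section 3.0).

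**Inputs that are assumptions**
- *f*, the share of enrolled subjects whose implant fails, and *m*, the share of implanted subjects whose device is malpositioned. The documents give neither for this study, so ranges are shown.

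**Plan's own figure.** The plan states no expected value, goal or precision for device success. The 343 comes from the effectiveness endpoint and does reproduce. An exact one-sample binomial test of 9% against 4.5% at one-sided 2.5% first reaches 80% power at n = 257 (success if at most 14 events; attained level 0.0241, power 81.5%), and 257/0.75 = 342.7, rounded up to 343. It serves here only as the denominator of the illustration.

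**Formulas**
- Planned rate = correctly positioned / implanted = 1 − m.
- Rate among enrolled = correctly positioned / enrolled = (1 − f)(1 − m).
- Gap = (1 − m) − (1 − f)(1 − m) = f(1 − m).

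The planned rate does not contain *f*. It is not 100% by definition, because malposition still lowers it, but it cannot respond to failed implants.

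**Numbers with 343 enrolled and m = 0**

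| Assumed f | Failed implants | Planned rate | Rate among enrolled |
|---|---|---|---|
| 0 | 0 | 343/343 = 100% | 343/343 = 100% |
| 2% | 7 | 336/336 = 100% | 336/343 = 98.0% |
| 5% | 17 | 326/326 = 100% | 326/343 = 95.0% |
| 8% | 27 | 316/316 = 100% | 316/343 = 92.1% |

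**With m = 2%** the planned rate is 98% throughout. The gap is 0, then 0.02 × 0.98 = 2.0 points, 0.05 × 0.98 = 4.9 points and 0.08 × 0.98 = 7.8 points for f = 0, 2%, 5% and 8%.

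**What the 40-patient figure can bear.** With no failures in 40, the upper end of the two-sided exact (Clopper-Pearson) 95% interval for the failure rate is 1 − 0.025^(1/40) = 8.8%. The one-sided 95% limit would be 1 − 0.05^(1/40) = 7.2%. On 343 subjects, 30 failures (8.7%) would give 313/343 = 91.3%. That result is therefore compatible with no gap and with one of up to about 9 points. It is not an estimate for this study.

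**The case against.** The strongest reply has five parts.

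- **Failed implants are not hidden.** They have their own category and forms, section 5.5 requires every enrolled subject to be accounted for, and they remain in the safety populations. A reader given both the enrolled and the implanted counts could work out the attempt-based rate. This stands, and it makes the defect a mis-specified summary and not a loss of data. The plan should still compute what its objective asks for.
- **Another statistic may cover it.** The annual CFDA report in section 13.2 lists procedure success. It has no definition, numerator or denominator and is not linked to Objective 3, so it does not fill the gap.
- **The link between endpoint and objective is inferred.** True: no sentence states it, and as a summary of position among implanted subjects the planned figure is not biased. But device success is the only listed endpoint that fits the objective; without that link, Objective 3 would have no endpoint.
- **Enrolled is not the only possible denominator.** Some enrolled subjects may never have had a device opened, so a device-attempted denominator is defensible. It would, however, omit failures that occur earlier in the procedure. Enrolled subjects are also not padded with patients never attempted: Table 2, footnote 1, leaves out anyone excluded on TEE whose procedure does not take place.
- **The endpoint is descriptive and the gap may be nil.** Both are correct, and both limit how much weight the point carries.

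**Conclusion.** The concern holds. As written, the planned proportion is the probability of correct position given an implant. It is insensitive to failed implants and does not estimate the implantation rate in Additional Objective 3.

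The overstatement, relative to a rate among enrolled subjects, is f(1 − m). Its actual size is unknown: nil if every implant attempt succeeds, and about 2 to 8 points for assumed failure rates of 2% to 8%. The conclusion that the statistic cannot respond to failed implants needs no assumed figure; only the illustrated sizes do.

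This should be corrected, but it does not threaten the study's main conclusions. The three primary analyses, the success criterion in section 13.4 and the sample size are unchanged.

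**What to change.** In section 13.2, replace the device success population with all enrolled subjects, as section 7.1 defines them. State that each enrolled subject with an unsuccessful implant counts as not a success, and report the number of such subjects. A rate among subjects in whom a device was attempted may be added as a labelled supplement from the device record in the Procedure eCRF; correct position among implanted subjects may be kept on the same terms. It would also help to define procedure success in the annual report and say how it relates to device success.

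The core change is one sentence. It needs no extra visits, data or subjects, since the Procedure, Out of service and Withdrawal eCRFs already cover these cases and section 13.1.1 already analyses enrolled subjects. Formally it is an amendment under section 15.0, with a justification and any ethics or regulatory notification required; otherwise it can be documented as a deviation from the statistical plan under section 13.7. The reported rate will be less favourable if any implants fail.
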